2.6.2.1 Summary of Safety in NCI-7845 (J-0669) FLAM in Newly-diagnosed Poor-risk AML

All-grade Tumor Lysis Syndrome was observed in 19/45 (42%), with one patient expiring due to disseminated intravascular coagulation (DIC) and multiorgan failure. Treatment-related mortality (TRM) at 30 days was observed in 2 patients (4%), with one patient each with TLS/DIC/multiorgan failure and fungal infection. TRM at 60 days was observed in 2 additional patients (4%), both died from sepsis. Adverse events Grade ≥ 3 included: 11% GI mucositis, 11% reversible SV arrhythmia with sepsis, 7% sepsis, 4% oral mucositis, and 4% diarrhea.

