2.6.2.3 Summary of Safety in NCI-8972 (J-1101) FLAM in Newly-diagnosed Poor-risk AML

In this comparison of FLAM vs. 7+3, adverse events were similar in both arms. Comparative adverse events Grade ≥ 3 included (FLAM, 7+3): febrile neutropenia (48%, 45%), infection (35%, 38%), hepatic dysfunction (21%, 23%), and GI events (11%, 9%).

Based on previous observations of Tumor Lysis Syndrome in prior AML studies of FLAM, preventive measures were included in this study including the use of allopurinol, phosphate binder, hydration, and rasburicase was allowed per institutional policy for hyperuricemia. The rates of TLS were similar between FLAM and 7+3 (FLAM: 8% versus 7+3: 7%). Treatment-related mortality was also similar between the arms at 30 days: FLAM: 5% versus 7+3: 2%, or at 60 days FLAM: 10% versus 7+3: 4%. The majority of early deaths (8/11 patients) on FLAM were >60 years.

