4. INVESTIGATIONAL PLAN

4.1 Overall Study Design

This is an open-label, multicenter, dose-escalation, safety and biomarker prediction study of alvocidib followed by 7+3 therapy in adults with newly diagnosed and previously untreated AML.

Induction – Alvocidib and 7+3

The starting dose of alvocidib will be 20 mg/m² as a 30-minute intravenous (IV) bolus followed by 30 mg/m² over 4 hours as an IV infusion administered daily on Days 1-3 of Induction. Patients will have a one day drug holiday (Day 4) before initiation of the 7+3 regimen. Beginning on Day 5, cytarabine will be administered as a 100 mg/m²/day continuous IV infusion for seven consecutive days (Days 5-11) plus daunorubicin administered at a dosage of 60 mg/m² via IV bolus of up to 15 minutes' duration on Days 5-7.

Escalation of the alvocidib dose will follow a standard 3+3 design with sequential cohorts of three patients treated with incrementally higher doses of alvocidib until a DLT is observed and the MTD is established. Three patients within a dose cohort may be enrolled without a waiting period between patients. Escalation to the next higher dose level will not occur until all patients within the current dose cohort have undergone full safety assessments (including count recovery or disease assessment).

If 1 of 3 patients in a cohort experiences a DLT, up to 3 additional patients will be treated at that dose level. If all patients in the expanded cohort have undergone full safety assessments (including count recovery or disease assessment) with no additional DLTs observed, the alvocidib dose will be escalated in a new cohort of 3 patients. If 2 or more of 3-6 patients at a given dose level experience a DLT during the first cycle, then the MTD will have been exceeded and up to a total of 6 patients will be treated at the previous lower dose level. If 0 or 1 of 6 patients experiences a DLT at this previous lower dose level, this dose will be declared the MTD.

The MTD is defined as the dose at which ≤1 of 6 patients experience a DLT during Cycle 1 with the next higher dose having at least 2 of 3-6 patients experiencing a DLT during Cycle 1.

The period of DLT determination for alvocidib and 7+3 ends at the start of consolidation therapy. However, any AEs that occur during Reinduction and meet DLT criteria will be taken into consideration when determining whether to escalate the dose of alvocidib and when defining the MTD.

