8.5 Serious Adverse Events and/or Adverse Events Requiring Discontinuation of Study Drug

Any serious adverse event (SAE) or unexpected AE \geq NCI CTCAE Grade 3 that occurs during this study and up to 30 days after discontinuation of study drug must be reported to the Study Medical Monitor within 24 hours of the Principal Investigator’s awareness of the event, whether or not this reaction is considered to be associated with use of the investigational drug.

In addition, the occurrence of any AE leading to permanent discontinuation of study drug must also be reported to the Sponsor within 24 hours of the Principal Investigator’s awareness of the event.

Serious adverse events must be scanned and emailed to the Sponsor/Study Medical Monitor.

It is expected that the Principal Investigator will provide or arrange appropriate supportive care for the study patient. A patient experiencing a serious adverse event(s) should be followed clinically until the event is resolved, deemed stable or permanent, or the patient starts another treatment for their disease. All telephone and scanned/emailed reports must be followed with a written Serious Adverse Event (SAE) report form within 24 hours of the Principal Investigator's awareness of serious adverse events and nonserious events which required discontinuation of study drug.

The (SAE) report form should be completed and signed by the Principal Investigator, scanned, and sent by email to the Sponsor as described above. The SAE Report Form is distinct and separate from the adverse event form included in the case report form.

Grades for all SAEs and AEs, regardless of whether they trigger expedited reporting or not, must still be captured by the CRF.

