8.7 Patient Deaths

Every effort will be made in the case of patients who die to determine the cause of death. Information regarding a patient who dies more than 30 days after receiving study drug may be recorded on a Death Report Form (no SAE report is required). An SAE report is recorded only if the event leading up to the patient's death began within 30 days of the last administration of study drug.

The Death Report Form is distinct and separate from the adverse event form included in the case report form.

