11.3.4 Safety Analyses

The following safety analyses will be performed on all patients who receive at least one dose of study drug.

- **Adverse Events** = Reported adverse event (AE) terms will be mapped to MedDRA preferred terminology. All reported events will appear in AE listings, however only treatment-emergent adverse events will be summarized. A treatment-emergent adverse event (TEAE) is an AE that starts or increases in severity any time after the first administration of any study drug up to 30 days following the last administration of any study drug. AE severity will be rated by the investigator according to NCI CTCAE version 4.03.
- **Clinical Laboratory Assessments** = Laboratory test results measured on a continuous scale and changes from baseline values will be summarized by visit and within alvocidib dose level using mean, standard deviation, median, minimum and maximum values. Categorical test results will be summarized within alvocidib dose level using shift tables. Additionally, for tests where NCI CTCAE, version 4.03, severity criteria are specified, NCI CTCAE severity grades will be summarized in shift tables.

- **Vital Signs** = Vital signs and changes from baseline values will be summarized by visit and within alvocidib dose level using mean, standard deviation, median, minimum and maximum values.

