7.10.2. Adverse Events

Reported adverse event (AE) terms will be mapped to MedDRA preferred terminology. AEs suggestive of tumor lysis syndrome (TLS) will be flagged based in the standardized MedDRA query (SMQ) for TLS. All reported events will appear in AE listings, however only treatment-emergent adverse events will be summarized. A treatment-emergent adverse event (TEAE) is an AE that starts or increases in severity any time after the first administration of any study drug up to 30 days following the last administration of any study drug. AE severity was rated by the investigator according to Common Terminology Criteria for Adverse Events (CTCAE) version 4.03 criteria.¹³

A high-level safety summary will display the numbers of patients within and across alvocidib dose levels who experience one or more AEs in each of the following categories:

- All TEAEs regardless of severity or presumed relationship to study drug
- TEAEs judged related to study drug
- All TLS SMQ TEAEs
- TLS SMQ TEAEs judged related to study drug
- Treatment-emergent serious adverse events (SAEs)
- TEAEs leading to a delay in the administration of study drug
- TEAEs leading to a reduction in the protocol-specified dose of study drug
- TEAEs leading to discontinuation of study drug
- TEAEs leading to withdrawal from the study
- TEAEs leading to death

The base summary of TEAEs will show incidence rates for each MedDRA primary SOC and/or PT by highest reported CTCAE severity grade and overall. A separate summary

will be produced each of the AE subsets listed above. Additional AE summaries may be produced using safety data from subsets of patients and/or characterized using additional SMOs.

Partial start and end dates for adverse events will be replaced by calendar dates that maximize the duration of the adverse event. The following steps will be followed.

For a partial start date:

- 1. Replace a missing month with January
- 2. Replace a missing calendar day with the first of the month
- 3. If the replacement date is prior to the first dose of study drug, then set the adverse event start date equal to the date of the first dose

For a partial end date:

- 1. Replace a missing month with December
- 2. Replace a missing calendar day with the last day of the month

The replacement date for a missing end date may exceed end of the adverse event reporting period specified in the study protocol.

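### A single TEAE window closes on Day 41 for induction-only patients but runs through every HiDAC cycle for others, so the AE tables by alvocidib dose have no common induction period

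*Protocol*

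**What the plan says.** Both documents use one rule. Protocol 11.3.4 lets the TEAE window run from the first dose "up to 30 days following the last administration of any study drug". SAP 7.10.2 agrees: a TEAE starts or worsens "any time after the first administration of any study drug up to 30 days following the last administration of any study drug". Protocol 11.3.4 adds: "All reported events will appear in AE listings, however only treatment-emergent adverse events will be summarized". SAP 7.10.2 summarises TEAEs, treatment-emergent SAEs and TEAEs leading to death within and across alvocidib dose levels. In SAP Table 3 no AE incidence table is split by treatment phase; only tumor lysis syndrome has a Cycle 1 table.

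Other safety periods run on different clocks:

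- **DLTs.** Protocol 4.1: "The period of DLT determination for alvocidib and 7+3 ends at the start of consolidation therapy". Section 4.4.3 sets the cytopenia criteria at 50 days after one induction cycle and 60 days after two.
- **Visits.** AEs are assessed at hematologic recovery or Day 50 (±3) in 5.2.6, and at recovery or Day 60 (±3) after reinduction in 5.3.1. The safety follow-up in 5.6.1 falls 30 days after the last dose.
- **Mortality.** Protocol 7.1 adds all-cause mortality at 30 and 60 days. SAP 7.10.1 takes it from the Kaplan-Meier curve for overall survival.
- **SAE reports.** Under 8.5, SAEs during the study and "up to 30 days after discontinuation of study drug must be reported". Under 8.7, an SAE report is made only if the event leading to the patient's "death began within 30 days of the last administration of study drug". Section 8.3 counts any death as serious, and 8.6 asks for later events reasonably associated with study drug.

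Protocol 4.1 expects that some patients will not consolidate.

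**The concern.** The primary objective is safety and tolerability over a range of alvocidib doses. The AE tables serve it only if each dose level is observed over a comparable period that covers the toxicity of alvocidib plus induction chemotherapy. The single window works against this in two directions.

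For patients who never consolidate, it closes while the protocol still treats the patient as under induction safety observation. A possibly related fatal event starting on Day 45 in a patient without recovery could be a DLT, yet be absent from the TEAE, treatment-emergent SAE and fatal-TEAE summaries.

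For patients who consolidate, it stays open through HiDAC. Events from cycles without alvocidib are then tabulated under the alvocidib dose given months before. If the share of patients consolidating, or the number of cycles, differs between dose levels, AE rates will differ for that reason alone.

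**Working it through.** The documents state the 30-day rule and the dosing days but no closing day, so there is no figure of theirs to reproduce. The check is study-day arithmetic.

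**Inputs**

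- Last induction dose: cytarabine, Day 11 (protocol 4.3.2).
- Last reinduction dose: cytarabine on cycle Day 9 (4.3.2).
- Last HiDAC dose: cycle Day 5, for up to four cycles (4.3.2).
- Start of HiDAC: at recovery or within 90 days of it (5.4).
- Cytarabine counts as study drug (SAP section 3).

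**Induction only**

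- Close = 11 + 30 = Day 41 (Day 42 if counted from the end of the last 24-hour infusion).
- Gap to the Day 50 visit: 50 − 41 = 9 days; with the ±3-day allowance, 47 − 41 = 6 to 53 − 41 = 12.
- Gap to Day 60: 60 − 41 = 19 days.

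**Induction plus reinduction, no HiDAC**

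If reinduction starts on study Day S, the last cytarabine is on S + 8 and the window closes on S + 38. The protocol gives no start day; Day 14 to 21 is assumed.

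| S | Last cytarabine | Close | Gap to Day 60 |
|---|---|---|---|
| 14 | 22 | 52 | 8 |
| 17 | 25 | 55 | 5 |
| 21 | 29 | 59 | 1 |

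The gap is zero at S = 22 and does not exist for later starts.

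**With HiDAC**

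With start day S, c cycles and cycle length L, close = S + (c − 1)L + 4 + 30. Cycle length is not given; 28 to 42 days is assumed.

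| S | c | Close, L = 28 | Close, L = 42 |
|---|---|---|---|
| 50 | 2 | 112 | 126 |
| 50 | 4 | 168 | 210 |
| 140 (Day 50 + 90) | 4 | 258 | 300 |

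One TEAE table can therefore mix a 41-day window with windows of about 168 to 300 days, roughly four to seven times as long (168/41 = 4.1; 300/41 = 7.3).

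**Which events fall in the gap**

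Only patients without consolidation are affected, because a later HiDAC dose keeps the window open. For them the DLT period has no stated end; it is taken here as recovery, or Day 50, or Day 60 if reinduced. Protocol 8.4 records an event once, at its highest grade, with dates spanning the whole event. An event that begins by Day 41 and becomes fatal on Day 45 therefore keeps its early start date and remains a TEAE. A Grade 4 cytopenia that becomes a DLT at Day 50 will normally have begun well before Day 41. What is missed is mainly first onset after the window closes.

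**The case against.** The strongest defence is that a 30-day post-dose window is clear, identical in both documents and applied to descriptive tables without hypothesis tests. SAP 7.10.2 allows additional AE summaries, related TEAEs are tabulated separately, and SAP 7.10.4 summarises laboratory values within cycle. This stands in part: the rule is usable as written. But the optional summaries are by subsets of patients, not by treatment period, and none is planned for induction.

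A reader might also infer four stronger things, which the documents do not support:

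- **That DLT counts, the MTD or 60-day mortality are compromised.** DLTs are judged under 4.1 and 4.4.3 without reference to the TEAE flag, and mortality comes from overall survival.
- **That no SAE report is needed for a fatal event starting after Day 41.** Section 8.7 read alone suggests it. Yet 8.3 counts any death as serious, 8.5 covers events during the study, and 8.6 asks for later drug-associated events. This is a conflict to reconcile, not a settled gap in reporting.
- **That earlier trials measure the loss.** For NCI-7845, protocol 2.6.2.1 says "TRM at 60 days was observed in 2 additional patients (4%), both died from sepsis"; in NCI-8972, FLAM treatment-related mortality rose from 5% at 30 days to 10% at 60. These figures date deaths, not onsets, and their interval starts before Day 41. Moreover, 4.4.3 excludes infections as DLTs. In NCI-8237 recovery ranged to Day 71 (ANC) and Day 80 (platelets), but the medians were 33 and 30 days, at lower thresholds than this trial's.
- **That consolidation is already known to differ by dose.** The SAP Appendix 2 sample table shows 13 of 22 patients (59%) with no HiDAC cycle, and at least one cycle in 2 of 3 at 20/30 against 4 of 13 at 30/60. But 8 of the 13 withdrawal reasons at 30/60 are missing and time on study there is at most 12.3 weeks, so it looks like an unfinished extract.

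**Conclusion.** The point holds as a mismatch between the TEAE summaries and the question of safety by alvocidib dose. For an induction-only patient the summarised period ends 9 days (6 to 12) before the Day 50 assessment. After reinduction it ends 1 to 8 days before Day 60 under the assumed start. For patients who consolidate, induction and HiDAC toxicity are pooled over a far longer period. How many events are lost or added cannot be estimated from the documents.

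The conclusion rests on cytarabine being a study drug. SAP section 3 says it is, although the same list names mitoxantrone and omits daunorubicin. Protocol 9.1 calls alvocidib the investigational study drug, and 8.5 and 8.7 use the singular. On an alvocidib-only reading the SAE limit in 8.7 would fall on Day 33 (3 + 30). If that reading also governed the TEAE rule, its window would close on Day 33 or, after reinduction, 30 days after the last alvocidib dose, and the HiDAC pooling would disappear. The words referring to any study drug in both TEAE definitions point the other way.

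This is a worthwhile, inexpensive improvement to the safety tables. It is not a flaw in dose escalation or in the mortality endpoint.

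**What to change.** Keep the TEAE definition. Add to protocol 11.3.4 and SAP 7.10.2 an induction-period summary of TEAEs, SAEs and fatal AEs by alvocidib dose:

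- Count onset or worsening from first dose to the start of consolidation. Without consolidation, count to the later of 30 days after the last dose and the end of the DLT period (recovery, or Day 50, or Day 60 if reinduced).
- Flag events after the start of other AML therapy, but do not remove them. A cut at that point would drop events now counted: a patient starting other therapy on Day 25 is currently counted to Day 41.
- Tabulate consolidation-period events separately.
- State which drugs count as study drug, since the closing day depends on it.

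Reconcile 8.7 with 8.3, 8.5 and 8.6 so that fatal events within the DLT period are reported consistently.

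The cost is one period flag, additional tables, possibly a few more SAE reports and slightly higher reported induction AE rates. Patients who stay on study without recovery are already seen weekly (5.2.4), so they need no new visits. For a patient who leaves earlier, new events are not actively sought after the 30-day visit in 5.6.1. Covering the rest of the period would take a contact or record check; otherwise the table should state where observation stopped.

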12. PROTOCOL AMENDMENTS

Any permanent change to the protocol must be handled as a protocol amendment. Protocol amendments will be written by the Sponsor. All protocol amendments must be submitted in writing to the Institutional Review Board (IRB)/Independent Ethics Committee (IEC), and the Principal Investigator must await IRB/IEC approval of the amendments before implementing the changes. However, a protocol change that is intended to eliminate an apparent immediate hazard to patients may be implemented immediately and the IRB/IEC is to be notified within five (5) days. The Sponsor should also be notified by telephone as soon as possible, ideally before the amendment is implemented and definitely within 5 days. The Sponsor will submit protocol amendments to the Regulatory Authorities.

When an amendment to the protocol substantially alters the study design and/or increases the potential risk to the patient, the currently approved written informed consent form will require similar modification and IRB/IEC approval. In such cases, repeat written informed consent will be obtained from patients currently enrolled in the study before expecting continued participation.

13. MONITORING

Prior to enrolling any participants, a study initiation visit (SIV), including protocol training, will be conducted for the study center. A Study Manual of Procedures will be provided to each clinical site. A record of site personnel training will be maintained by the site onsite training logs.

Clinical Research Associates (CRAs) and other applicable personnel will receive training prior to study initiation about the disease, applicable Standard Operating Procedures (SOPs), the protocol and other study-specific items. Team organization, communication, and operational issues will also be discussed.

The conduct of the study will be closely monitored by representatives (Clinical Research Associates "CRAs" or study monitors) of the Sponsor or designee, to verify adherence to the Protocol, ICH GCP guidelines, and applicable regulations. The CRA will verify eCRF entries by comparing them with Sponsor/site-generated source documents, hospital, clinic, office and/or study records which will be made available for this purpose. CRAs will monitor the study as outlined in the Monitoring Plan prepared for the study.

During the study, CRAs will visit the clinical sites to assess and assure satisfactory enrollment rate, data recording, and maintenance of required regulatory documentation, drug accountability, and compliance with the protocol. CRAs will also be able to monitor the data remotely. The Investigator will ensure that all requested materials, including subject charts, eCRFs, source documents, laboratory records, and drug inventory records, will be available to the CRA. At the end of the study, a closeout visit (COV) will be performed.

The Investigator will allow Sponsor's representatives, designee and/or and any regulatory agency to have direct access to all study records, eCRFs, corresponding subject medical records, test product dispensing records and test product storage area, and any other documents considered source documentation. The Investigator also agrees to assist the representative, if required.

14. AUDITING

The study is conducted under the sponsorship of Tolero Pharmaceuticals, Inc, in compliance with the applicable international and local regulatory requirements as well as applicable ICH guidelines, Helsinki (1964, 1975, 1983, 1989, 1996, 2000, 2002, 2004, 2008, 2013) and in respect of the Sponsor or designee's SOPs for study conduct and monitoring.

Audits may be carried out by Sponsor representatives, and inspection may be performed by regulatory authorities' inspectorate or IRBs/IECs before, during, or after the study. The Investigator will allow and assist Sponsor's representatives and any regulatory agency to have direct access to all study records, eCRFs, subject medical records, study product dispensing records and study product storage area, study facilities, and any other documents considered source documentation.

For the Audit(s) performed by, or on behalf of, Sponsor's auditors, audit certificate(s) will be provided by Quality Assurance.

15. ETHICS AND RESPONSIBILITY

15.1 Principal Investigator's Responsibilities

The Principal Investigator shall ensure that all work and services described herein, or incidental to those described herein, shall be conducted in accordance with the highest standards of Good Clinical Practice (GCP). The Principal Investigator shall administer the investigational drug only to patients under his/her personal supervision, or under the supervision of any Sub-Investigator(s) responsible to him/her, who are identified on the Form FDA 1572/Regulatory Authorities approval form. The Principal Investigator will provide copies of the study protocol, amendments, and investigational brochure to all Sub-Investigators, Pharmacists, or other staff responsible for study conduct.

With the exception of eliminating an immediate hazard to a subject, the Investigator should not deviate from the protocol or implement any changes without written prior approval from Sponsor and prior review and documented approval/favorable opinion from the IRB/IEC of an amendment.

Change(s) which involve(s) only logistical or administrative changes are authorized. The Investigator should document and explain any deviation from the protocol.

The Investigator is responsible for adequate and safe medical care of subjects during the trial and for ensuring that appropriate medical care and relevant follow-up procedures are maintained after the trial. Any additional data from these follow-up procedures must be documented and available to Sponsor who will determine whether or not the data need to be documented in the case report forms.

